4. LIST OF ABBREVIATIONS AND DEFINITIONS OF TERMS

The following abbreviations and specialist terms are used in this study protocol.

Abbreviation or Specialist Term	Explanation
AE	Adverse event
AESIs	Adverse Events of Special Interest
AIDS	acquired immunodeficiency syndrome
ALT	Alanine aminotransferase
AML	Acute myeloid leukemia
ANC	Absolute neutrophil count
AUC	Area under the concentration-time curve
β-hCG	beta-human chorionic gonadotropin
B-ALL	B-cell Acute Lymphoblastic Leukemia
B-LBL	B-cell lymphoblastic lymphoma
BM	Bone marrow
BP	Blood pressure
CBC	Complete blood count
CKD-EPI	Chronic Kidney Disease Epidemiology Collaboration
C _{max}	Curve [AUC] and maximum concentration
CR	Complete response
CRF	Case report form
CSR	Clinical study report
CT	Computerized tomography
CTCAE	Common Terminology Criteria for Adverse Events
DDI	Drug-drug interactions
DLBCL	Diffuse large B-cell lymphoma
DNA	deoxyribonucleic acid
ECG	Electrocardiogram
ECOG	Eastern Cooperative Oncology Group
eCRF	Electronic case report form
eGFR	Estimated glomerular filtration rate
ES	Epithelioid sarcoma
ESC	External Safety Committee
EZH2	Enhancer of zeste homologue 2
FCBP	Females of childbearing potential
FL	Follicular lymphoma
FSH	Follicle-stimulating hormone

Abbreviation or Specialist Term	Explanation
GCP	Good Clinical Practice
GFR	glomerular filtration rate
GOF	Gain-of-function
H3K27	Histone 3 lysine 27
H3K27me3	Trimethylated state of histone 3 lysine 27
HATs	Histone acetyl transferases
HBV	Hepatitis B virus
HCV	Hepatitis C virus
HIV	Human immunodeficiency virus
HMTs	Histone methyltransferases
HR	Heart rate
IB	Investigator's Brochure
ICF	Informed consent form
ICH	International Conference on Harmonization
IEC	Independent Ethics Committee
IMP	Investigational Medicinal Product
INI1	Integrase interactor 1
IRB	Institutional Review Board
IUD	Intrauterine device
IUS	Intrauterine hormone-releasing system
MDS	Myelodysplastic syndrome
MedDRA	Medical Dictionary for Regulatory Activities
Min	Metastasis in prostate cancer
MLL2	Mixed lineage leukemia protein 2
MPN	Myeloproliferative neoplasms
MRI	Magnetic resonance imaging
NCI	National Cancer Institute
NCI CTCAE	National Cancer Institute Common Terminology Criteria for Adverse Events
NGS	next generation sequencing
NHL	Non-Hodgkin lymphoma
P-gp	P-glycoprotein
PK	Pharmacokinetics
QSR	Quarterly Safety Review
QTcF	QT interval corrected by Fridericia's formula
R/R	relapsed or refractory

Abbreviation or Specialist Term	Explanation
RNA	ribonucleic acid
SAE	Serious adverse event
SD	Standard deviation
SET	Sun(var)3-9, enhancer-of-zeste and trithorax
SMARCA4	SMARC, subfamily A, member 4
SOC	System organ class
SUSAR	Suspected unexpected serious adverse reaction
T	Temperature
$t_{1/2}$	half-life
T-ALL	T-cell acute lymphoblastic leukemia
TEAE	Treatment-emergent adverse event
TESAE	Treatment-emergent serious adverse event
T-LBL	T-cell lymphoblastic lymphoma
T_{max}	To maximum plasma concentration
ULN	Upper limit of normal
WBC	White blood cell
WT	Wild-type

5. INTRODUCTION

This document is a protocol for a human research study. This study is to be conducted according to: United States and international standards of GCPs, FDA Title 21 Part 312, and International Council for Harmonisation of Technical Requirements for Pharmaceuticals for Human Use (ICH) guidelines; applicable government regulations; and institutional research policies and procedures.

5.1. Background

Post-translational modifications of histones, the core proteins of chromatin, play an important role in controlling the fidelity of cellular gene transcription patterns. One of the critical transcription-controlling histone modifications is methylation of specific lysine and arginine residues, catalyzed by histone methyltransferases (HMTs) which all use S-adenosyl methionine (SAM) as a co-factor for the methylation reaction (Copeland, 2013). Genetic alterations in a number of HMTs or associated regulatory proteins have been identified in several human cancers where they are purported to be oncogenic. Enhancer of zeste homolog 2 (EZH2) is the catalytic subunit of the multi-protein polycomb repressive complex 2 (PRC2) that catalyzes the mono-, di, and trimethylation of lysine 27 of histone H3 (H3K27) (Margueron, 2011).

Enhancer of zeste homolog-2 mutation and/or over-expression has been observed in several cancer types, leading to an aberrant H3K27 trimethylation (H3K27me3) state which is oncogenic (Chase, 2011). For instance, somatic EZH2 gain-of-function (GOF) mutations at three hotspots (Y646, A682, and A692 [NM_001203247]) are found in 10% to 20% of follicular lymphoma (FL) and diffuse large B-cell lymphoma (DLBCL). These GOF mutations result in an oncogenic dependency on EZH2 production of abnormally high H3K27me3 levels, and resultant transcriptional reprogramming of the cell (Morin, 2010).

5.1.1. Hematologic Malignancies

Somatic mutations within the EZH2 gene on 3 hotspots (Y646, A682, and A692 [NM_001203247]) are present in follicular lymphoma (FL) and diffuse large B-cell lymphoma (DLBCL) and lead to high levels of H3K27 trimethylation (H3K27me3) in these lymphomas. Those mutations of EZH2, therefore, have been proposed to be required for the development and maintenance of the mutation-bearing lymphomas. Inhibition of EZH2 leads to reduction in H3K27me3 and cell death in lymphoma cell lines bearing the mutation. In addition, loss of function of mixed lineage leukemia protein 2 (MLL2) and histone acetyl transferases (HATs) may generate abnormal methylation states of H3K27, potentially leading to a dependency on EZH2. In nonclinical models, inhibition of EZH2 leads to reduction in H3K27me3 in all lymphoma cell lines irrespective of their EZH2 mutation status. While cells with wild-type EZH2 are growth inhibited with EZH2 inhibition in vitro, only mutant bearing cells undergo cell death in culture (Beguelin, 2013; Knutson, 2014).

Changes to the tumor microenvironment, for instance those affecting antitumor immunity, are increasingly recognized as an important mechanism in lymphomagenesis, affecting all types of NHL (Scott, 2014). Epigenetic therapy has been suggested to release repression of molecules important for immune recognition on tumor cells (Wrangle, 2013), and EZH2 inhibition may induce similar effects. In addition, loss of EZH2 has been described as affecting T helper cell plasticity (Tumes, 2013) and is proposed to inhibit the function of regulatory T cells (Arvey,

2014; DuPage, 2015; Yang, 2015), suggesting that EZH2 inhibition may contribute to enhancing antitumor immunity.

In summary, the available nonclinical data suggest that EZH2 mutant lymphomas should show the highest sensitivity to EZH2 inhibition, but wild-type cases could also be affected through tumor cell autonomous mechanisms (mutations in MLL2, HATs, ubiquitously transcribed tetratricopeptide repeat, X chromosome [UTX], etc) and/or effects of EZH2 inhibitors on the tumor microenvironment.

5.1.2. Solid Tumors

In addition to the EZH2 GOF activation mutations described above, overexpression or amplification of EZH2 has been described in numerous tumor types, including but not limited to bladder, breast cancer, colorectal, lung, pancreatic, ovarian, prostate, mesothelioma, uveal melanoma, renal carcinoma, cholangiocarcinoma, and stomach cancer (Kuroki, 2014; LaFave, 2015; Comet, 2016). This is partially explained by the regulation of EZH2 gene expression by the pRB-E2F pathway, which is dysregulated in many tumor types (Bracken, 2003). In many of these tumors, EZH2 has been demonstrated to function as an oncogene (Comet, 2016). For instance, EZH2 overexpression promotes anchorage-independent growth and cell invasion in breast cancer (Kleer, 2003), proliferation and epithelial-mesenchymal transition in lung cancer (Takawa, 2011; Tiwari, 2013), and tumorigenesis and metastasis in prostate cancer (Min, 2010).

These data suggest that inhibition of EZH2 might also be beneficial in solid tumors that overexpress EZH2 or contain amplifications of the EZH2 gene.

5.2. Tazemetostat

5.2.1. Nonclinical Pharmacology

Tazemetostat (EPZ-6438) is a highly selective small molecule inhibitor of the histone-lysine methyltransferase EZH2 gene. Tazemetostat inhibits both wild-type (WT) and mutant EZH2 mutated at residues Y641, A677G and A687 with half maximal inhibitory concentrations (IC₅₀) ranging from 2-38 nmol/L. The compound shows a 36-fold selectivity over the most closely related HMT, EZH1, and greater than a 4500-fold selectivity over other HMTs. It selectively inhibits intracellular H3K27 methylation in a concentration- and time- dependent manner in all cell lines tested in vitro to date.

Additional details are provided in the current tazemetostat Investigator's Brochure (IB).

5.2.2. Pharmacokinetics

Tazemetostat is orally bioavailable in subjects with hematologic and solid tumor malignancies. The absorption is rapid with a median time to maximum plasma concentration (t_{max}) of 1 to 2 hours. The mean absolute bioavailability was approximately 33% (Study EZH-103). In dose escalation studies in subjects with hematologic and solid tumor malignancies, tazemetostat exhibited a more than dose-proportional increase in exposure (area under the concentration-time curve [AUC] and maximum concentration [C_{max}]). At the recommended therapeutic dose of 800 mg twice daily, the mean steady state C_{max} was 829 ng/mL and AUC from 0 to 12 hours (AUC₀₋₁₂) was 3340 ng•hr/mL. The consistent t_{max} and apparent elimination half-life (t_{1/2}) across the

range of doses evaluated (100 to 1600 mg twice daily) suggest overall dose-independent absorption and clearance.

There was no difference in relative bioavailability between low-fat and high-fat meal conditions. A high-fat meal exhibited a negligible effect on the extent and rate of absorption. A high-fat meal showed a 24% and 18% decrease in tazemetostat C_{max} and AUC exposures, while the geometric mean ratios for C_{max} and AUC for the major metabolite EPZ-6930 were close to 1, thereby demonstrating that a similar overall systemic exposure was seen after a high-fat meal compared to dosing in the fasted state.

There was little to no accumulation (C_{max} and AUC) of plasma tazemetostat following repeat dosing, likely due to auto-induction. The metabolite EPZ-6930 had minimal accumulation following multiple dosing. Tazemetostat is eliminated primarily via hepatic metabolism in humans, with approximately 88% bound to plasma proteins. Following administration of a single oral 800 mg dose of radiolabeled tazemetostat, the average percent recovery of the administered dose was 15.4% in urine and 87.8% in feces. Unchanged tazemetostat accounted for 1.39% of the administered dose recovered in urine and was not detected in feces.

5.2.3. Pharmacodynamics

Predose and postdose skin punch biopsies were successfully collected in 32 subjects enrolled in the dose-escalation part of Study E7438-G000-101. A dose-dependent reduction in trimethylation of lysine 27 on histone H3 (H3K27me3) was observed across the stratum spinosum layer of the skin, with a marked decrease in H3K27me3 as tazemetostat AUC₀₋₁₂ increased after administration of doses ranging from 100 to 800 mg twice daily. The reduction in H3K27me3 appeared to reach a plateau in the AUC₀₋₁₂ observed in the 800 mg twice daily dose cohort. An inhibitory maximum effect (E_{max}) model-predicted decrease in H3K27me3 at the observed mean AUC₀₋₁₂ on Day 15 in the 800 mg twice-daily dose cohort was more than 80% of the maximum effect, indicating that target inhibition in the skin was near maximal and that doubling the dose to 1600 mg twice daily resulted in only a modest incremental increase in the inhibition of H3K27 methylation. These pharmacodynamic results informed the determination of 800 mg twice daily as the tazemetostat recommended phase 2 dose (RP2D).

5.2.4. Effect of Other Drugs on Exposure to Tazemetostat

A thorough investigation for drug interaction potential was done by conducting a series of in vitro studies which included CYP phenotyping, metabolic stability, substrate and inhibition assessment of metabolic transporters, and inhibition of major human CYP enzymes. Based on the results from the population PK analyses, the impact of concomitant drugs on tazemetostat exposure was evaluated. These results demonstrate that CYP3A4 inhibitors, CYP3A4 inducers, CYP2D6 inhibitors, CYP2D6 inducers and pH modifiers had no clinically significant effect on tazemetostat exposure suggesting that these drugs may be co-administered with tazemetostat **CCI**. With respect to potential drug-drug interactions (DDI) associated with drug transporters, tazemetostat is a P-glycoprotein (P-gp) substrate but not a substrate for other drug transporters studied, including breast cancer resistance protein, organic anion transporting polypeptide (OATP) 1B1 and 1B3, organic anion transporters 1 and 3, organic cation transporter 2, and multidrug and toxin extrusion 1. However, P-gp does not seem to limit tazemetostat absorption in subjects, presumably due to the relatively good passive permeability

at the therapeutic dose of 800 mg twice daily. This suggests that tazemetostat is not susceptible to transporter-mediated DDI as a victim drug.

5.2.5. Effect of Tazemetostat on Exposure to Other Drugs

Tazemetostat is eliminated primarily via hepatic metabolism in humans. In vitro test systems using hepatic preparations from mice, rats, dogs, rabbits, monkeys, and humans suggest that tazemetostat forms similar metabolites across species. The results of in vitro phenotyping studies indicate that CYP3A4 is the predominant enzyme responsible for tazemetostat metabolism in humans. With respect to tazemetostat as a perpetrator, although tazemetostat inhibits several CYPs in vitro, based on the inhibitory constant (K_i) and the observed tazemetostat exposure in subjects at the therapeutic dose of 800 mg twice daily, the potential clinical implications due to the inhibitory potential of tazemetostat on drugs that are substrates of CYP3A4, CYP2C8, or CYP2C19 is limited. Notably, the effect of tazemetostat on CYP3A4 is complicated with opposing induction and time-dependent inhibition of the enzyme. The net clinical DDI outcome is a weak induction of CYP3A as indicated by an approximately 40% reduction of midazolam AUC following 800 mg twice daily dosing for 15 days (Study E7438-G000-101). While tazemetostat may potentially inhibit P-gp, OATP1B1, and OATP1B3, there is limited potential for clinically significant DDI with substrates of these transporters, based on in vitro transporter inhibition assessment and observed exposures at the recommended dose regimen of 800 mg twice daily. The 3 major metabolites are not expected to affect the activities of the major human CYPs and major drug transporters.

5.3. Study Rationale

Tazemetostat is metabolized primarily by CYP3A4. Inhibition or induction of CYP3A4 in vivo is expected to result in increased or decreased systemic exposure to tazemetostat respectively. Therefore, Part 1 of this study will determine the effect of a strong CYP3A4 inhibitor, itraconazole, on tazemetostat PK. Likewise, Part 2 of the study will determine the effect of a strong CYP3A4 inducer, rifampin, on tazemetostat PK.

5.4. Clinical Experience

CCI

Tazemetostat is under investigation in clinical trials for the treatment of:

- non-Hodgkin lymphoma (NHL), including diffuse large B-cell lymphoma (DLBCL) and follicular lymphoma (FL).
- CCI
- CCI
- integrase interactor 1 (INI1) or switch/sucrose nonfermentable (SWI/SNF)-related, matrix-associated, actin-dependent regulator of chromatin (SMARCA4)-deficient tumors in both adult and pediatric populations (including synovial sarcoma, rhabdoid tumors, renal medullary carcinoma, epithelioid sarcoma [ES], other INI1- or SMARCA4-deficient tumors).

- Prostate cancer

- CCI [REDACTED]

- CCI [REDACTED]

- CCI [REDACTED]

5.5. Benefit:Risk Assessment

5.5.1. Clinical and Nonclinical Safety Profile

Based on nonclinical toxicology studies and the clinical experience as of 12 April 2021, this section summarizes the anticipated safety profile for tazemetostat.

Among the 895 adult and pediatric subjects treated with tazemetostat monotherapy, 857 (96%) subjects experienced at least 1 treatment-emergent adverse event (TEAE), with 597 (70%) subjects experienced TEAEs assessed as related to the study drug by the Investigator. Of subjects with TEAEs, 469 (55%) subjects had TEAEs of Grade 3 or 4 severity. Treatment-related grade 3 or 4 TEAEs occurred in 161 (34%) of subjects with grade 3 or 4 TEAEs.

The following treatment-emergent AEs, regardless of causality, have been observed in $\geq 10\%$ of adult subjects across clinical studies: nausea, fatigue, vomiting, diarrhea, anemia, decreased appetite, asthenia, dyspnea, constipation, thrombocytopenia, and abdominal pain.

The most common treatment-related treatment-emergent AEs in the adult subjects across clinical studies include: nausea, fatigue, asthenia, anemia, diarrhea, vomiting, thrombocytopenia, decreased appetite, neutropenia, and alopecia.

Of the 779 adult subjects receiving tazemetostat monotherapy, 326 (42%) experienced at least one treatment-emergent serious adverse event (TESAE). Treatment-related SAEs were reported in 58 (7%) of subjects. Of the 109 pediatric subjects, 52 (48%) experienced a TESAE, and 10 pediatric subjects (9%) experienced a TESAE that was assessed as related by the Investigator.

Of the 895 adult and pediatric subjects, 144 (16%) subjects died within 30 days of last dose of tazemetostat. Of the 144 deaths, 135 (94%) of the deaths were due to disease progression. In addition, 2 deaths, one that was due to intestinal obstruction and one with an unknown cause, were assessed as possibly treatment related by the Investigator.

Of the 109 pediatric subjects, 30 (28%) died on study within 30 days of last dose and 28 (93%) of those deaths were due to disease progression.

The most common TEAEs leading to tazemetostat dose interruption in the adult population were thrombocytopenia (5%), neutropenia (3%), and anemia and diarrhea (each 2%). The most common TEAEs leading to tazemetostat dose reduction across all populations were thrombocytopenia, neutropenia and diarrhea reported in $<1\%$ of adult subjects.

As of 12 April 2021, 7 (0.5%) myeloid AESI have been reported in an estimated cumulative exposure of 1,521 patients from both clinical and post-marketing sources. The risk of myeloid neoplasia as a result of EZH2 inhibition is considered uncertain based on available literature and Epizyme clinical data. A risk mitigation plan is in place to exclude potential subjects who may be predisposed to developing a myeloid neoplasia and for early identification and monitoring of subjects who may be developing a myeloid neoplasia.

In addition, as described in [Section 5.4](#) and more extensively in [Section 12.4.2](#) AESIs identified for the tazemetostat development program include: T-LBL/T-ALL, MDS, AML, and other myeloid malignancies like MPN. Epizyme considers the risk for T-LBL/T-ALL in tazemetostat clinical trials to be largely concentrated in pediatric subjects. One event of T-LBL has occurred in pediatric subjects (n=109). The risk of T-LBL/T-ALL in adults is not known; however, the incidence of treatment-related T-LBL/T-ALL in adults is expected to be uncommon. As of 12 April 2021, over 954 subjects (adults and pediatric) have been treated with tazemetostat as monotherapy and in combination with no other reported cases of T-LBL/T-ALL.

As tazemetostat is a bromide salt, bromide levels were measured in the phase 1 study of tazemetostat in adults (Study E7438-G000-101) and pediatric subjects (Study EZH-102). As of 12 April 2021, bromide elevation was reported in 5 (5%) of 109 pediatric subjects, all of which were considered to be related to tazemetostat treatment, but there were no associated AEs suggestive of bromide toxicity.

Additionally, there are unknown risks of abnormal pregnancy outcomes and drug-drug interactions. Based on the nonclinical toxicology of tazemetostat, the potential risks associated with treatment include: T-LBL, bone changes, bile duct hyperplasia, lymphoid depletion, teratogenicity and phototoxicity.

Further details of study designs, tazemetostat exposure, and AESI are outlined in the current IB.

5.5.2. Conclusion

Tazemetostat is a clinically active drug that has the potential to benefit both adult and pediatric subjects across different tumor types, including non-Hodgkin's lymphoma (NHL) and INI1-negative solid tumors where there are unmet medical needs. The safety of tazemetostat has remained favorable across the clinical development program in more than 895 subjects. See [Appendix 4](#) for details regarding benefit/risk assessment during the COVID-19 pandemic.

6. TRIAL OBJECTIVES AND PURPOSE

6.1. Study Objectives and Endpoints

Objective	Endpoint
Part 1: Tazemetostat and Itraconazole	

Primary
 
 To evaluate the effect of CYP3A4 inhibition by itraconazole on the steady-state pharmacokinetics (PK) of tazemetostat when administered as a single and twice daily oral dose in subjects with advanced malignancies 	
 AUC_{0-t}: area under the plasma concentration-time curve from time 0 to the time of the last quantifiable concentration AUC₀₋₇₂: area under the plasma concentration-time curve from time 0 to 72 hours post-dose C_{max}: observed maximum plasma concentration

Secondary
 
 To evaluate the steady-state safety profile of tazemetostat when co-administered as a single and twice daily oral dose with itraconazole in subjects with advanced malignancies 	
 Safety parameters: Adverse event assessment, physical examination, vital signs (blood pressure, heart rate, body temperature), 12-lead ECG, clinical laboratory tests (hematology including coagulation profile, serum chemistries, urinalysis), ECOG performance status, and concomitant medication monitoring

 To evaluate the steady-state PK of tazemetostat and its metabolites after administration alone and with itraconazole To evaluate the effect of itraconazole on PK of a single 400 mg oral dose of tazemetostat. 	
 AUC_{0-t}: area under the plasma concentration-time curve from time 0 to the time of the last quantifiable concentration C_{max}: observed maximum plasma concentration T_{max}: observed time at C_{max} λz: terminal phase elimination rate constant t_{1/2}: terminal elimination half-life
Part 2: Tazemetostat and Rifampin	

Primary
 
 To evaluate the effect of CYP3A4 induction by rifampin on the steady-state PK of tazemetostat when administered as a single and twice daily oral dose in subjects with advanced malignancies. 	
 AUC_{0-t}: area under the plasma concentration-time curve from time 0 to the time of the last quantifiable concentration AUC₀₋₄₈: area under the plasma concentration-time curve from time 0 to 48 hours post-dose C_{max}: observed maximum plasma concentration

Objective	Endpoint

Secondary
 
 To evaluate the steady-state safety profile of tazemetostat when co-administered as a single and twice daily oral dose with rifampin in subjects with advanced malignancies. 	
 Safety parameters: Adverse event assessment, physical examination, vital signs (blood pressure, heart rate, body temperature), 12-lead ECG, clinical laboratory tests (hematology including coagulation profile, serum chemistries, urinalysis), ECOG performance status, and concomitant medication monitoring

 To evaluate the steady-state PK of tazemetostat and its metabolites after administration alone and with rifampin. 	
 AUC_{0-t}: area under the plasma concentration-time curve from time 0 to the time of the last quantifiable concentration C_{max}: observed maximum plasma concentration T_{max}: observed time at C_{max} λ_z: terminal phase elimination rate constant t_{1/2}: terminal elimination half-life

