
Study drug, dosage, and mode of administration:
 
Part 1: Tazemetostat and itraconazole
 
Subjects in Part 1 of the study will receive a single oral dose of 400 mg tazemetostat on day 1, 15, and day 36. The subjects will receive tazemetostat (oral 400 mg dose) tablets to be taken twice daily from day 3 – 14 and day 21 – 35.
 
Part 2: Tazemetostat and rifampin
 
Subjects in Part 2 of the study will receive a single oral dose of 800 mg tazemetostat on day 1, 15 and day 24. The subjects will receive tazemetostat (oral 800 mg dose) tablets to be taken twice daily from day 3 – 14 and day 17 – 23.
 
The subjects will be requested to maintain a medication diary of each dose of tazemetostat. The dosing diary must be returned to the site staff at each visit.

Other medications, dose, and mode of administration: Itraconazole and Rifampin
 
Part 1: Tazemetostat and Itraconazole
 
Subjects will receive itraconazole (oral 200 mg dose) to be taken daily from day 18 – 38.
 
Part 2: Tazemetostat and Rifampin
 
Subjects will receive rifampin (oral 600 mg dose) to be taken daily on day 17 – 25.

Duration of treatment for tazemetostat:
 
Part 1: Tazemetostat and Itraconazole

Subjects in Cycle 1 Part 1 of the study will be treated for 39 days. On day 1, 15, and 36, subjects will receive a single dose of 400 mg tazemetostat. On day 3 – 14, and from 21 – 35, subjects will receive a twice daily dose of 400 mg tazemetostat.

Part 2: Tazemetostat and Rifampin

Subjects in Cycle 1 Part 2 of the study will be treated for 26 days. On day 1, 15, and 24 subjects will receive a single dose of 800 mg tazemetostat. On day 3 – 14, and from 17 – 23, subjects will receive a twice daily dose of 800 mg tazemetostat.

Criteria for evaluation:

Pharmacokinetics: Plasma tazemetostat and EPZ 6930 concentrations will be determined for both single and multi-dose and the following parameters will be calculated, as data permit:

- AUC_{0-t} : area under the plasma concentration-time curve from time 0 to the time of the last quantifiable concentration
- AUC_{0-24} : area under the plasma concentration-time curve from time 0 to 24 hours post-dose
- AUC_{0-48} : area under the plasma concentration-time curve from time 0 to 48 hours post-dose
- AUC_{0-72} : area under the plasma concentration-time curve from time 0 to 72 hours post-dose
- C_{max} : observed maximum plasma concentration
- T_{max} : observed time at C_{max}

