7.3. Treatment Assignment

After obtaining written, informed consent, subjects with advanced malignancies will be screened according to the exclusion and inclusion criteria. Subjects who have complied with all selection criteria will receive a unique subject number upon enrollment in the study. Subject numbers will be allocated sequentially in the order in which subjects are enrolled. The Investigator or designee will enter the corresponding subject number and complete each eCRF.

Subjects will be assigned to the study as follows:

Part 1: Tazemetostat and Itraconazole Drug Interaction ([Figure 2](#))

Part 2: Tazemetostat and Rifampin Drug Interaction ([Figure 3](#))

Part 1: Tazemetostat and Itraconazole Drug Interaction

Subjects in Part 1 of the study will receive a single oral, 400 mg dose of tazemetostat on Day 1, 15, and Day 36. The subjects will receive tazemetostat (oral 400 mg dose) tablets to be taken twice daily from Day 3 – 14 and Day 21 – 35. In addition, the subjects will receive oral 200 mg itraconazole once daily from Day 18 – 38. Detailed schedule of assessments is provided in [Table 3](#).

Note: Subjects will not be dosed with tazemetostat on day 2, from day 16 – 20, 37, and 38.

Part 2: Tazemetostat and Rifampin Drug Interaction

Subjects in Part 2 of the study will receive a single, oral, 800 mg dose of tazemetostat on Day 1, 15 and Day 24. The subjects will receive tazemetostat (oral 800 mg dose) tablets to be taken twice daily from Day 3 – 14 and Day 17 – 23. In addition, the subjects will receive oral 600 mg rifampin once daily from Day 17 – 25. Detailed schedule of assessments is provided in [Table 4](#).

Note: Subjects will not be dosed with tazemetostat on day 2, 16, and 25.

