9.5. Treatment of Overdose

In the event of an overdose of tazemetostat (defined as administration of more than the protocol-specified dose), the Investigator should contact the Medical Monitor, or their designee immediately and closely monitor the subject for AEs/SAE and laboratory abnormalities.

For reference, five half-lives of tazemetostat would be at minimum 25 hours, longer in subject with delayed clearance. Decisions regarding dose interruptions or modifications will be made by the Investigator in consultation with the Medical Monitor or their designee based on the subject's clinical evaluation.

A plasma sample for PK analysis may be requested on a case-by-case basis. If requested, the plasma sample should be collected at least within 7 days from the date of the last dose of study treatment.

The quantity of the excess dose as well as the duration of the overdosing should be documented in the eCRF. Refer to section 12.1 for details of recording and reporting overdose, medication errors, misuse, and abuse.

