13.2. PK analyses

Plasma concentrations of tazemetostat and its metabolite (EPZ6930) will be determined by validated bioanalytical methods. Plasma concentrations of tazemetostat and its metabolite (EPZ6930) will be listed for each subject and summarized by study part, treatment, day, and nominal time. Standard summary statistics will be calculated (ie, arithmetic mean, geometric mean, standard deviation, median, minimum, and maximum) for each endpoint.

All PK parameters will be calculated with noncompartmental methods using actual times. The following PK parameters will be determined as data permit:

Part 1: Plasma AUC₀₋₇₂, C_{max}, T_{max}, and t_{1/2} for tazemetostat alone on Day 15 – 18, and in the presence of itraconazole on Day 36 – 39.

Part 2: Plasma AUC_{0-48} , C_{max} , T_{max} , and $t_{1/2}$ for tazemetostat alone on Day 15 – 17, and in the presence of rifampin on Day 24 – 26.

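### The steady-state objective has no AUC0-12: the named AUCs add a washout tail, so they would overstate the fold-change if half-life moves with exposure

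*Protocol*

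**What the plan says.** Protocol 6.1 and SAP 2.1 set the primary objective as the effect of itraconazole or rifampin on steady-state tazemetostat PK. The primary endpoints are AUC0-t, Cmax and, for Part 1, the "area under the plasma concentration-time curve from time 0 to 72 hours post-dose"; Part 2 uses 0-48 h. The shortest AUC window listed anywhere is in the Synopsis: "area under the plasma concentration-time curve from time 0 to 24 hours post-dose".

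Protocol 13.2 fixes the Part 1 comparison: "for tazemetostat alone on Day 15 – 18, and in the presence of itraconazole on Day 36 – 39". Part 2 compares Days 15-17 with Days 24-26. Days 15, 36 and 24 are single morning doses that end a twice-daily run. Section 7.3 then withholds drug in Part 1: "Subjects will not be dosed with tazemetostat on day 2, from day 16 – 20, 37, and 38". In Part 2 there is no tazemetostat on Days 2, 16 and 25.

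AUC0-12 appears only as background. Section 5.2.2 reports that steady-state Cmax at 800 mg twice daily "was 829 ng/mL and AUC from 0 to 12 hours" was 3340 ng·h/mL, and 5.2.3 relates the pharmacodynamic response to the same measure. SAP 1 and 17.1 leave PK analysis to a separate PK analysis plan, which was not available for review.

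**The concern.** On the comparison days, hours 0-12 are a steady-state dosing interval and everything after 12 h is washout. AUC0-72 and AUC0-48 (and AUC0-t when drug is quantifiable beyond 12 h) therefore add a tail whose size depends on half-life. AUC0-24 does not cure this, because hours 12-24 are also off drug. Under linear PK the steady-state AUC0-12 equals the single-dose AUC to infinity. The longer window after repeated doses equals neither, because it also collects carry-over from earlier doses.

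The fold-change is the study's main result. If an inhibitor lengthens half-life, the tail grows on the test day and the ratio is too high. If an inducer shortens it, the ratio is too low. As listed, no AUC ratio would answer the steady-state question or sit directly beside the Protocol's own AUC0-12 figure.

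**Working it through.** **The plan's own figures.** SD of the log difference = √ln(1.09) × √(2 × (1 − 0.80)) = 0.186. With n = 12 and 90% confidence limits inside 80-125%, paired equivalence power is 89.1% at a ratio of 1.06 and 87.9% at 0.94. This matches the stated 88%. The passage refers only to tazemetostat AUC, so it is not tied to a window.

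**Two indications of half-life.**
- Section 9.5: "five half-lives of tazemetostat would be at minimum 25 hours, longer in subject with delayed clearance". 25/5 = 5 h or more.
- Section 5.2.2: Cmax/Cavg = 829 × 12/3340 = 2.98. In a linear one-compartment oral model with assumed absorption rate constant ka = 1.5/h, half-lives of 3, 5 and 6 h give 2.13, 1.65 and 1.53. With ka up to 3.0/h, the most that 3 h gives is 2.40. Solving for 2.98 over ka 0.75-3.0/h gives an effective half-life of about 1.1-2.2 h.

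**Tail factor.** With instant absorption, AUC0-∞/AUC0-12 after the last dose is 1/(1 − e^(−12k)). At 5 h this is 1/(1 − 2^(−2.4)) = 1.23, and at 6 h it is 1.33. With ka = 1.5/h and exact superposition (24 earlier twice-daily doses before Day 15), AUC0-72/AUC0-12 is 1.257 at 5 h and 1.361 at 6 h.

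**First pass.** Section 5.2.2 states "The mean absolute bioavailability was approximately 33" per cent. Write F = Fg × Fh = 0.33 for gut and liver, with Fg between 0.5 and 1.0 (assumed), Fg = 1/(1 + g), Fh = 1/(1 + x) and elimination rate proportional to x/(1 + x). One factor s scales x and g, and is solved so that the AUC0-12 ratio equals the true ratio R.

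For R = 2.0 and Fg = 1: x = 1/0.33 − 1 = 2.03 and s = 0.5, so half-life rises by 2 × (1 + 0.5 × 2.03)/(1 + 2.03) = 1.33. From 5 h it becomes 6.65 h, where the tail factor is 1.430. AUC0-72 then reads 2 × 1.430/1.257 = 2.28. For Fg = 0.5 half-life rises 1.41-fold.

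The test days follow 30 earlier doses (Day 36) or 14 (Day 24). Ranges are over Fg:

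| Basis for half-life | ka (/h) | t½ (h) | AUC0-72/AUC0-12 | True 2.0 reads (AUC0-72) | True 0.50 reads (AUC0-48) |
|---|---|---|---|---|---|
| Fit to 5.2.2 | 0.75 | 1.14 | 1.003 | 2.015-2.020 | 0.499 |
| Fit to 5.2.2 | 1.5 | 1.75 | 1.012 | 2.05-2.06 | 0.496-0.497 |
| Fit to 5.2.2 | 3.0 | 2.20 | 1.026 | 2.08-2.10 | 0.491-0.493 |
| Section 9.5 minimum | 1.5 | 5 | 1.257 | 2.275-2.342 | 0.456-0.469 |
| Above that minimum | 1.5 | 6 | 1.361 | 2.315-2.390 | 0.448-0.464 |

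If only first pass changes, the tail factor is the same on both days and cancels.

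**At the planning ratios.** As a bound, put the whole effect on half-life with a 5 h reference and ka = 1/h. Then 1.06 reads 1.086 and 0.94 reads 0.918. Power to conclude no effect falls from 89% to 79% and from 88% to 78%.

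**The case against.** The case on the other side has four parts.

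1. Section 9.5 is a reference remark on overdose monitoring, and the steady-state data in 5.2.2 imply a much shorter effective half-life. In a linear model, 5-6 h would also mean 1.23- to 1.33-fold accumulation, while 5.2.2 reports little to none (attributed there to likely auto-induction). This stands, and it means the small end of the range must be shown.
2. Cmax is also primary and has no tail, and the listed t½ would reveal a change in half-life. This stands, but neither supplies the steady-state AUC ratio.
3. The PK analysis plan may already derive AUC0-12. That is possible, but it would not alter the endpoints written in Protocol 6.1 and SAP 2.1.
4. Replacing the primary AUCs is out of proportion to a shift of about 0-5% at the fitted half-life. This stands.

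A reader might infer that the reported interaction will be 14-20% too high and that the error exceeds the sampling uncertainty. The 90% interval spans about ×/÷ exp(1.796 × 0.186/√12) = 1.10. The Part 1 shift exceeds that only at 5-6 h, half-lives that do not reproduce the Cmax and AUC0-12 in 5.2.2.

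**Conclusion.** The mismatch is certain: the objective is steady-state exposure, no AUC0-12 is listed, and every listed AUC on the comparison days can include washout. The direction is conditional. Ratios move away from 1 if half-life moves with exposure, stay unbiased if only first pass changes, and would err the other way if half-life moved against exposure.

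The size is unsettled. A true 2.0 reads about 2.02-2.10 and 0.50 about 0.49-0.50 at the half-life fitted to 5.2.2, against 2.28-2.39 and 0.45-0.47 at 5-6 h. The 2.0 and 0.50 are illustrations, not figures from the documents. The model is linear with one compartment. A biphasic profile could leave a larger tail than the fit suggests, since 829 and 3340 are means. The more than dose-proportional exposure and likely auto-induction described in 5.2.2 are not modelled.

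A reader might infer a risk of wrongly declaring no interaction. The documents do not support that, because a shift away from 1 makes the 80-125% criterion harder to meet. Nor do they require the named primary AUCs to be demoted. Severity is minor to moderate.

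**What to change.** Add AUC0-12 to Protocol 6.1 and 13.2, SAP 2.1 and the PK analysis plan. Report its geometric mean ratio with 90% confidence interval for Day 36 against Day 15 (Part 1) and Day 24 against Day 15 (Part 2), and base the steady-state fold-change statement on it. AUC0-72, AUC0-48 and AUC0-t may remain named endpoints, reported as including washout.

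The cost is one more noncompartmental parameter and a text amendment. All samples to 12 h are already scheduled on these days, and Protocol 11.1 requires the 12 h sample before any dose due then. No new samples, visits or subjects are needed.
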